10.5.1.1 Dose Limiting Toxicities

The analysis of dose limiting toxicities (DLT) will be based on the DLT Analysis Set defined in [Section 7.3](#). A listing and summary of the subject incidence of dose limiting toxicities (DLT) during period 1 will be provided should they occur.

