### Cycle 1/Period 2:

The aim of Period 2 will be to assess the MTD as derived from Period 1, or the maximum tested dose, if MTD has not been reached, for additional safety and preliminary efficacy data in an expanded cohort of up to 15 evaluable subjects receiving SC treatment only (no cIV run-in) [Figure 2](#).

Doses for Cycle 1/Period 2 will be derived based on PK, bioavailability, and safety data collected in Cycle 1/Period 1 and DLRT review and recommendations. Subjects will receive sequentially the estimated SC doses equivalent to the 9  $\mu\text{g}/\text{day}$  cIV in week 1, SC doses equivalent to the 28  $\mu\text{g}/\text{day}$  cIV **starting in week 1 and continuing into week 2**, and then the SC doses of the selected maximal dose **and dosing interval from Cycle 1/Period 1 starting in week 2 (day 12) and continuing to complete a total of 6 weeks of blinatumomab** (see [Section 6.2.1.2.2](#) for definition of the DLT evaluation period **for Period 2**).

**Sample Size:** Six DLT evaluable subjects will be enrolled at each SC dose level in Cycle 1/Period 1. Subjects may be replaced. This sample size is based on practical considerations and is consistent with conventional phase 1 oncology studies. If the true DLT rate is 10%, there is a 89% probability of observing  $\leq 1$  DLT and 11% probability of observing 2 or more DLT in 6 subjects. If the true DLT rate is 30%, the probability of observing  $\leq 1$  DLT decreases to 42% and probability of observing 2 or more DLT increases to 58%.

Up to 15 evaluable subjects will be enrolled into Cycle 1/Period 2 with the planned target treatment dose being the highest tolerable dose regimen or highest tested dose regimen based on DLRT's recommendations. Continuous toxicity monitoring for early termination of the trial in Cycle 1/Period 2 will be performed. Termination of Cycle 1/Period 2 will occur if the posterior probability that the DLT rate is greater than 25% is at least 80%.

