MTD will be defined as the highest dose level at which  $\leq 1$  of 6 subjects experience a DLT. If no subject experiences a DLT, the MTD will be defined as the maximal dose tested.

For further details see [Section 6.2.1.2.1](#) and [Section 6.2.1.2.3](#).

Approved

### 3.1.2 Cycle 1/Period 2

The aim of Period 2 will be to assess the MTD as derived from Period 1, or the maximum tested dose, if MTD has not been reached, for additional safety and preliminary efficacy data in an expanded cohort of up to 15 evaluable subjects receiving SC treatment only (no cIV run-in) [Figure 2](#).

Doses for Cycle 1/Period 2 will be derived based on PK, bioavailability, and safety data collected in Cycle 1/Period 1 and DLRT review and recommendations. Subjects will receive the estimated SC equivalent doses **of the 2 lower cIV doses as given in the cIV blinatumomab run-in period sequentially: 2 doses of the equivalent SC dose to 9 µg/day of cIV during week 1, 3 doses of the equivalent SC dose to 28 µg/day cIV starting in week 1 and continuing into week 2, and then the SC MTD (or the maximum tested dose if MTD is not reached) and SC dosing interval as determined in Cycle 1/Period 1 starting in week 2 (day 12) and continuing to complete a total of 6 weeks of blinatumomab. See [Section 6.2.1.2.2](#) for definition of the DLT evaluation period for Period 2.**

**Continuous toxicity monitoring for early termination of the trial in Cycle 1/Period 2 will be performed. Termination of Cycle 1/Period 2 will occur if the posterior probability that the DLT rate is greater than 25% given the cumulative data thus far is at least 80%.**

The study endpoints are defined in [Section 10.1.1](#) and stopping rules are detailed in [Section 10.2](#).

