### 3.4 Replacement of Subjects

Subjects enrolled may be replaced if they are not evaluable for DLT during the DLT observation period as described in [Section 6.2.1.2.2](#).

#### 3.4.1 Replacement Rules in Cycle 1/Period 1

Subjects may be replaced for any of the following reasons:

- failing to complete all 3 cIV dosing levels during cIV run-in (weeks 1 to 3)
- failure to receive **all doses (q48h, q72h, q96h, or q7d dosing)**, at least 4 of the 5 doses (q24h dosing), or at least 8 of 9 doses (q12h dosing) during the SC treatment period (week 4)
- withdrawal from study for DLT without having had PK assessments (subjects who withdraw due to DLT are evaluable from a safety standpoint, but may not be evaluable from a PK standpoint if they have not completed their PK blood draws)
- subjects may be replaced if they miss the PK assessment time point and are unable to resume dosing and PK assessments
  - Note: Subjects who miss a dose before any PK assessments will default to the day of the missed dose. PK assessments will be performed per [Table 4](#) following the subject's resumed dose of investigational product (IP). For example, if a subject misses the dose on study day 2, the restart treatment day will be considered as study day 2 and all applicable assessments will be done per Schedule of Assessments (refer to [Table 3](#) and [Table 4](#) for further details)
- for all subjects who miss PK samples, the PK scientist will evaluate the PK results for this subject, and determine if the subject needs to be replaced, or if the PK results are sufficient for analysis. The DLRT will be informed of this decision to replace or not replace individual subjects at the time of the DLRT meeting.
  - subjects who do not complete PK assessments may continue on study, even if replaced

#### 3.4.2 Replacement Rules in Cycle 1/Period 2

Subjects may be replaced for any of the following reasons (except subjects removed for DLT that will never be replaced):

- failure to receive **at least 85% of the first 8 planned doses during the SC treatment period as outlined in [Table 6](#) (this would include 5 doses of step dose run-in and 3 doses at MTD)**

Approved

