## 10.4 Planned Methods of Analysis

### 10.4.1 General Considerations

A clinical study report will be generated for the final analysis. All documented parameters will be adequately evaluated. The data will be summarized overall, and by assigned dose cohort using suitable descriptive measures. Individual data will be listed.

The DLT findings during Period 1 will be tabulated.

Descriptive statistics for demographic, safety, PK parameters, and biomarker data will be summarized by dose, dose schedule, and time as appropriate. The PK parameters will be estimated with non-compartmental analysis. For categorical variables, the number and percentage of subjects in each category will be summarized. Continuous variables will be summarized by n, mean, standard deviation, median, Q1 (25th percentile), Q3 (75th percentile), minimum, and maximum values.

Point estimates for efficacy endpoint incidences will be accompanied by 2-sided 95% exact binomial confidence intervals (CIs) ([Clopper CJ, Pearson ES, 1934](#)).

When data are summarized by time, the values recorded against the scheduled time points listed in the protocol will be used. When assessing minimum/maximum increases or decrease over the study, all assessments including unscheduled assessments will be used. In general, data listings will be sorted by dose, subject, and time.

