One or more dosing regimens (refer to Dosing Schema Figure 1 in protocol) may be selected based on clinical findings including safety, tolerability, and PK results from previous cohorts; and after Dose Level Review Team (DLRT) review and make recommendations for the next SC cohort dose and frequency. The dose may be increased (by 1 dose level or between the dose of the previous cohort and the next higher dosing level in Figure 1 schema in protocol), kept at the same dose level or decreased by 1 or more dose levels. The dose frequency chosen (q12h, q24h, q48h,

q72h, q96h, or q7days) will be decided by the DLRT and will be based on the previous cohort PK data.

Once the SC dosing is complete, a treatment free period of 2 to not more than 3 days between stopping SC and restarting cIV will be observed. Then the cIV blinatumomab dosing will resume at 112 µg/day (weeks 5 to 6) to complete 6 weeks of treatment.

For each SC dose cohort, if ≤ 1 of the 6 DLT evaluable subjects experience a DLT during the SC administration DLT evaluation period then the dose will be determined to be tolerable and the DLRT will decide the next dose level to be initiated and the frequency of administration for the next cohort; see Section 6.2.1.2.2 in protocol for definition of the DLT evaluation period.

For each SC dose cohort, if ≥ 2 of the 6 DLT evaluable subjects experience a DLT during the SC administration then dosing will stop for individual subjects who experience a DLT, a DLRT meeting will be conducted, and further steps will be determined, such as dose de-escalation or increasing dosing interval (Figure 1 in protocol). In addition, if subjects on this cohort have not reached the SC dosing, they will be allowed to stay on study but will finish cycle 1/period 1 as cIV.

MTD will be defined as the highest dose level at which ≤ 1 of 6 subjects experience a DLT. If no subject experiences a DLT, the MTD will be defined as the maximal dose tested.

For further details, see Section 6.2.1.2.1 and Section 6.2.1.2.3 of protocol.

3.1.2 Cycle 1/Period 2

The aim of Period 2 will be to assess the MTD as derived from Period 1, or the maximum tested dose, if MTD has not been reached, for additional safety and preliminary efficacy data in an expanded cohort of up to 15 evaluable subjects receiving SC treatment only (no cIV run-in).

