4.1 Study Endpoints

4.1.1 Primary Endpoint

- Subject grade, incidence, and severity of dose limiting toxicities (DLTs) and adverse events

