- If cycle 2 is given: experienced a DLT during the entire duration of the SC administrations and 16 days following the last SC dose or until the start of cycle 2 (whichever is longer), up to 30 days after the last SC dose or treated with blinatumomab at 112 µg/day cIV for 42 days.

Dose Limiting Toxicity (DLT)

The occurrence of any of the toxicities mentioned in the section 6.2.1.2.3 of the protocol will be considered a DLT, if judged by the investigator to be related to administration of blinatumomab.

ECOG Performance Status Assessment

ECOG performance status assessment will be performed using the ECOG score. For more details please refer appendix C in Protocol.

End of Study for Individual Subject

End of IP Administration for subjects who had blinatumomab is defined as the date the decision was made to end IP as recorded on the End of IP CRF page.

End of Treatment

Defined as the last assessment for the protocol-specified treatment phase of the study for an individual subject.

End of Follow-up

Defined as the date that the last subject completes the last protocol-specified assessment in the study.

Enrollment Date

Enrollment Date is defined as the date of enrollment collected on the CRF.

Subject Level End of Study (EOS) Date

End of study for each subject is defined as the date the subject last completed a protocol-specified procedure. The date will be recorded on the End of Study CRF page.

Investigational Product

The term 'investigational product' is used in reference to blinatumomab.

Last Dose Date of Investigational Product

This is the stop date of the last dose of blinatumomab administration reported on the Investigational Product Administration CRF.

Maximum Tolerated Dose (MTD)

MTD will be defined as the highest dose level at which ≤ 1 of 6 subjects experience a DLT. If no subject experiences a DLT, the MTD will be defined as the maximal dose tested.

Optional Cycle 2

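### Final DLT reporting is planned for Period 1 only, although DLTs are a primary endpoint in both periods, and the documents do not say how the MTD is reported if Period 2 stops for toxicity

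*SAP*

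**What the plan says.** The primary endpoint in SAP 4.1.1 is "Subject grade, incidence, and severity of dose limiting toxicities (DLTs) and adverse events". Protocol 10.1.1.1 has the same endpoint, and neither names a period.

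The planned final output is narrower. SAP 10.5.1.1 says: "A listing and summary of the subject incidence of dose limiting toxicities (DLT) during period 1 will be provided should they occur". Protocol 10.4.1 says: "The DLT findings during Period 1 will be tabulated". SAP 11 declares no departures from the protocol.

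The other DLT provisions cover both periods. The DLT Analysis Set (SAP 7.3, Protocol 10.1.2.3) takes every DLT-evaluable subject. SAP 6 gives evaluability criteria for Period 2. Protocol 6.2.1.2.2 and SAP 8.1.1.2 set the windows: week 4 (7 days) in Period 1, and in Period 2 56 days, extendable, if Cycle 2 follows, or 70 days if it does not.

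On the MTD, SAP 6 says: "MTD will be defined as the highest dose level at which ≤ 1 of 6 subjects experience a DLT". SAP 3.1.2 gives the aim of Period 2 as "to assess the MTD as derived from Period 1", for further safety and preliminary efficacy. Protocol 10.2 and SAP 3.1.3 stop Period 2 once the posterior probability of a DLT rate above 25% reaches 80%. No section connects such a stop to the reported MTD.

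**The concern.** Period 2 DLTs are defined, collected and acted on during the trial, but no final analysis reports them. A reader of the final report would see a DLT incidence that comes only from a 7-day SC week after three weeks of cIV dosing. The 56 to 70 day experience of subjects who start on SC dosing would have no DLT figure.

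The adverse event tables cannot stand in. DLT status under Protocol 6.2.1.2.3 depends on relatedness, persistence, time to resolution and a list of exceptions. The tables in SAP 10.5.1 are by system organ class, preferred term and worst grade, use the full analysis set, and are not created where two or fewer subjects have the event. The DLRT output list in SAP Appendix F includes adverse events but no DLT listing.

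The second gap concerns the MTD, a secondary endpoint. Its definition uses a count out of 6 from Period 1, and Period 2 has its own toxicity boundary. If the two disagree, the documents do not say what the report states.

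**Working it through.** **1. Share of the DLT data without a planned summary.** Inputs: about 30 evaluable subjects in Period 1 and up to 15 in Period 2 (SAP 3.2); windows of 7 days and of 56 to 70 days (SAP 8.1.1.2).

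- Subjects: 15 / (30 + 15) = 33%.
- Period 1 observation: 30 × 7 = 210 subject-days.
- Period 2 observation: 15 × 56 = 840 to 15 × 70 = 1050 subject-days.
- Share in Period 2: 840 / 1050 = 80% to 1050 / 1260 = 83%.

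This assumes full enrolment and full windows. With only 5 Period 2 subjects and 56-day windows, the share is 280 / (210 + 280) = 57%.

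**2. The plan's own figures, reproduced.** For Period 1, P(at most 1 of 6) = (1−p)^6 + 6p(1−p)^5. At p = 0.10 this is 0.531 + 0.354 = 0.886 (stated 89%). At p = 0.30 it is 0.118 + 0.303 = 0.420 (stated 42%).

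For Period 2, the rule stops at r DLTs in n subjects if P(rate > 0.25) under Beta(0.5 + r, 1.5 + n − r) is at least 0.80. Every boundary in Protocol Table 10 (SAP Table 1) reproduces; the closest case is 3 of 7, with posterior 0.7996. An exact recursion with looks at n = 5 to 14 reproduces Protocol Table 11 (SAP Table 2):

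| True DLT rate | P(stop), stated | P(stop), computed | Average n, stated | Average n, computed |
|---|---|---|---|---|
| 20% | 17% | 17.4% | 13.7 | 13.69 |
| 25% | 30% | 30.3% | 12.7 | 12.73 |
| 30% | 45% | 44.9% | 11.6 | 11.60 |
| 40% | 72% | 72.4% | 9.3 | 9.25 |
| 50% | 90% | 90.2% | 7.3 | 7.32 |
| 60% | 98% | 97.8% | 6.1 | 6.06 |

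**3. How often the two rules can disagree.** The joint probability is P(pass Period 1) × P(stop Period 2). It assumes one regimen, the same true DLT rate in both periods, independent periods and no DLRT discretion.

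| True DLT rate | P(pass Period 1) | P(stop Period 2) | Joint |
|---|---|---|---|
| 20% | 0.655 | 0.174 | 11% |
| 25% | 0.534 | 0.303 | 16% |
| 30% | 0.420 | 0.449 | 19% |
| 40% | 0.233 | 0.724 | 17% |

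These are joint probabilities. Given that a regimen has passed Period 1, the probability of a Period 2 stop is the third column, so 45% at a 30% rate.

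**4. How far apart the results would be.** The lowest observed rate that meets a Table 10 boundary is 5/13 = 38%. The highest that qualifies a Period 1 dose as the MTD is 1/6 = 17%.

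**The case against.** The best defence is that Period 2 DLTs are not ignored. They have their own window and evaluability criteria, they drive the stopping rule, and SAP 8.1 brings DLTs in all subjects into every enrolment and dosing decision. The DLRT can de-escalate or end dosing. Period 2 subjects are in the adverse event tables, and Protocol 10.4.1 promises individual listings. SAP 10.5.1.1 itself opens by basing the DLT analysis on a set with no period limit. All of this is correct, and it means that the omission does not weaken safety monitoring. It still leaves no named final output that shows which Period 2 subjects had a DLT, or at what incidence.

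A reader might infer more than the documents support:

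- *That Period 2 exposure is un-primed.* It lacks a cIV run-in, but it has five SC step doses before the MTD dose on day 12 (Protocol 3.1.2 and 3.4.2) and mandatory dexamethasone (Protocol 6.2.1.3).
- *That a regimen stopped in Period 2 will still be reported as the MTD.* This follows only from a literal reading of the definition plus silence elsewhere; no section says it.
- *That the MTD rests on the Period 1 DLT count alone.* Protocol 3.1 says that PK and bioavailability are used together with the DLT data.
- *That the expected 20% loss measures selection for tolerance in Period 1.* Protocol 3.3 applies it to both periods and to several reasons, including subject request.

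A short escalation window followed by an expansion cohort is the declared design, and this point does not dispute it.

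**Conclusion.** The reporting gap stands on the text of both documents. One component of the primary endpoint has no planned final analysis for up to 15 of about 45 evaluable subjects and about 80% of planned DLT observation time, in the only part that tests SC dosing without a cIV run-in.

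The MTD point holds in a limited form: the definition and the Period 2 stopping rule are not reconciled. The chance that they disagree is 11% to 19% for true DLT rates of 20% to 40%, under the assumptions in step 3. The equal-rate assumption is doubtful, because the windows differ so much. If the Period 1 rate were 10% and the Period 2 rate 20% to 50% (both assumed), the joint probability would run from 15% to 80%, so no single figure from that range should be relied on.

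A reader might also conclude that the MTD label should lapse automatically at a Table 10 boundary. The documents do not settle that. Such a rule would trigger 17% of the time at a true DLT rate of 20% and 30% of the time at 25% (Protocol Table 11), and a rate of 25% does not exceed the protocol's own threshold. It is a design choice for the sponsor.

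**What to change.** 1. In Protocol 10.4.1 and SAP 10.5.1.1, remove the restriction to Period 1. Plan a DLT listing and subject incidence with an exact 95% confidence interval on the DLT Analysis Set, separately for each Period 1 cohort and for Period 2. For Period 2, refer to the evaluability criteria in SAP 6, because SAP 7.3 points to 8.1.1.2, which gives only the window. Describe the Period 2 interval as descriptive, since it does not allow for the stopping rule.
2. Reconcile the MTD definition (Protocol 3.1.1; SAP 3.1.1 and 6) with the Period 2 stopping rule. Report the Period 2 DLT incidence and any boundary crossing beside the MTD, and have the sponsor state in advance how the MTD is reported if Period 2 stops for toxicity.

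The cost is wording in two documents and one more table from data already collected. The downside for the sponsor is a possibly less favourable MTD statement.

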10.5.2 Laboratory Test Results

10.5.2.1 Chemistry, Hematology and Coagulation

Individual chemistry, hematology and coagulation laboratory data will be listed and may also be plotted for selected parameters. Values outside the normal laboratory reference ranges will be flagged as high or low on the listings. CTCAE grades will also be highlighted where appropriate. Unscheduled assessments will be incorporated in the laboratory analyses where possible.

The number and percentage of subjects experiencing treatment emergent laboratory toxicities with worst post dose CTCAE grades of ≥ 1 , ≥ 2 , ≥ 3 and 4 will be presented. The direction of the laboratory worsening will be denoted. The summary will be presented for all laboratory parameters for which at least one subject experienced a treatment emergent toxicity with a worst grade ≥ 3 .

Additionally, the number and percentage of subjects experiencing 1, 2, 3 and 4 worsening CTCAE grade shifts from baseline will be presented. The direction of the laboratory worsening will again be denoted.

Shifts tables indicating the change between the baseline and the maximum post dose CTCAE grades for an increased value, and the maximum post dose grade for a decreased value will be provided for selected laboratory parameters of interest.

A listing of CTCAE grade 3 or higher laboratory toxicities will be provided. This listing will include all laboratory data for the subject and laboratory parameter of interest in order to provide proper context. A flag will indicate the grade 3 or higher toxicity.

Summaries of the absolute value and/or changes from baseline at each scheduled assessment will be provided for selected laboratory parameters of interest.

A summary of the change from baseline to the post dose maximum, time to post-dose maximum, change from baseline to the post dose minimum, and the time to the post dose minimum may also be provided for selected parameters of interest.

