4.2 Planned Covariates

The relationship of the certain baseline covariates to endpoints will be explored if appropriate. Biomarker data may be incorporated in additional exploratory subgroup or multivariate analyses. The analyses of biomarkers may be performed after collection of all samples during the conduct of the study and therefore may be reported after the final analysis.

5. Hypotheses and/or Estimations

No formal statistical hypothesis will be tested.

The clinical hypothesis is that blinatumomab administered through the SC route will demonstrate a tolerable safety-profile with serum concentrations comparable to those for which efficacy was shown with cIV administration in subjects with indolent relapsed/refractory Non-Hodgkin's Lymphoma (NHL).

6. Definitions

Age at Enrollment

Subject age at enrollment will be collected in years in the clinical database.

Baseline

For the analysis of all endpoints, baseline will be defined as the value measured on day 1 of the first cycle of blinatumomab. If a day 1 value is not available, the most recent value before the day of the start of any protocol-specified therapy may be used.

Best Overall Response

Best overall response for a subject is determined as ORR (CR+PR) using Cheson ([Appendix B](#)) and Lugano criteria ([Appendix C](#)) during the Safety Follow-up visit (2 to 4 weeks after the end of therapy for cycle 1). In the case where a second cycle is administered, the assessment has to be done prior to the start of the next cycle to assess the evolution of disease (as close to 2 weeks after the last dose of IP cycle 1, but before starting cycle 2).

Change From Baseline

Change from Baseline is the arithmetic difference between post-Baseline and Baseline values.

Disease Related Events

Disease Related Events are events (serious or non-serious) anticipated to occur in the study population due to the underlying disease eg, disease progression ([Table 3](#)). Such events do not meet the definition of an adverse event unless assessed to be more severe than expected for the subject's condition.

Disease Related Events that do not qualify as Adverse Events or Serious Adverse Events:

- An event which is part of the normal course of disease under study (eg, disease progression in oncology or hospitalization due to disease progression) is to be reported as a Disease Related Event.
- Death due to the disease under study is to be recorded on the event CRF.

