A subject may receive a second cycle of blinatumomab administered SC if the subject derived clinical benefit (demonstrated on staging scans) from Cycle 1/Period 2 treatment. If no clinical benefit occurred with SC in Cycle 1/Period 2 then an optional Cycle 2/Period 2 may still be given but will administered as a cIV infusion instead of SC. If blinatumomab is administered as a cIV infusion it will be dosed at 9 $\mu\text{g/day}$ cIV for 7 days for days 1 through day 7, next the dose will be escalated (dose step) to 28 $\mu\text{g/day}$ cIV for 7 days starting on day 8 through day 14, and then advanced to 112 $\mu\text{g/day}$ cIV for 28 days starting on day 15 through day 42.

Percent Change From Baseline

Percent change from Baseline is the arithmetic difference between post-Baseline and Baseline divided by Baseline values times 100.

Screened

A subject is considered in screening once a consent form has been signed.

Study Day 1

Study day 1 is defined as the first day of administration of the investigational product after enrollment. The day prior to Study Day 1 is considered Day -1.

Study Day

Post study day 1: study day= (date - date of Study Day 1) + 1

Pre study day 1: study day= (date – date of Study Day 1)

Study Duration

For an individual subject, the length of participation includes a 14 day screening period, up to a 14 week treatment period (6 weeks for cycle 1 in Period 1 and Period 2 and 6 weeks for the optional Cycle 2, separated by a 14 day treatment free interval), and a safety follow-up visit (30 days [+ 7 days] after the last dose of study treatment).

For subjects who complete the protocol from the date of first dose through optional Cycle 2, the entire duration of the study will take approximately 20 weeks to complete. However, individual study duration will vary depending on administration of a second cycle and tolerability of blinatumomab by an individual subject.

Treatment emergent adverse events (TEAEs)

A treatment emergent adverse event refers to the adverse event that starts on or after first dose of blinatumomab through 30 days after the last dose of blinatumomab. It is indicated by the flag whether an event start before first dose of blinatumomab on the Event CRF page. This reporting window also applies to treatment-emergent serious adverse events (SAEs).

7. Analysis Subsets

The analysis of all endpoints, unless noted otherwise, will be conducted on the Full Analysis Set defined in [Section 7.1](#).

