10.1 General Principles

Descriptive statistics will be provided for selected demographics, safety, immunogenicity, PK, PD, and biomarker data. Descriptive statistics on continuous measurements will include means, medians, standard deviations, and ranges, while categorical data will be summarized using frequency counts and percentages. Data will be summarized by dose cohort and by time as appropriate. Graphical summaries of the data may also be presented. When data are summarized by time, the scheduled time points listed in the protocol will be used). For statistical analyses comparing change from baseline, only subjects with both baseline and at least one post-baseline assessment will be included. When assessing minimum/maximum increases or decreases over the study, all assessments, including unscheduled assessments will be used.

The final analysis will be triggered when target enrolment is complete, and all subjects complete the study or withdraw from the study. The data will be analyzed once they have been entered, cleaned, and locked.

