10.5.1 Adverse Events

The Medical Dictionary for Regulatory Activities (MedDRA) version 19.0 or later will be used to code all adverse events to a system organ class and a preferred term.

The severity of each adverse event will be graded using CTCAE version 4.0 criteria. Subject incidence of treatment emergent events and treatment related treatment emergent events will further be summarized by worst severity grade.

Subject incidence of all treatment emergent, serious treatment emergent, treatment related, serious treatment related, those leading to withdrawal of investigational product or other protocol-required therapies, and fatal adverse events will further be tabulated by system organ class and preferred term for each dose cohort in descending order of frequency. The above adverse event tables will include disease related events and will not be created if two or fewer subjects in the study experience the adverse event. Similar summaries will be repeated for EOIs. Time to onset and duration of selected EOIs (infection and neurologic events) may also be summarized.

Subject incidence of disease related events and fatal disease related events will be tabulated by system organ class and preferred term for each dose cohort. All DREs and fatal DREs would be tabulated by system organ class and preferred term separately.

DREs should be included with AEs in any submission datasets, integrated summaries and in CTD reporting.

Tables with AEs as above will be produced for period 1 for SC and cIV dosing separately. Listings of any on-study deaths, including early withdrawals due to adverse events will be provided should they occur.

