10.5.6 Exposure to Investigational Product

Descriptive statistics will be produced to describe the exposure to investigational product by dosing schedule for cIV and SC separately. The number of cycles, number of doses of investigational product and the total dose in μg will be summarized.

Details for each blinatumomab administration will be listed for every subject. In addition, a listing of the unique manufacturing lot numbers, and a listing of the subjects administered each manufacturing lot number will be provided.

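### Period 1 hematology and chemistry worst-grade and shift tables mix cIV and SC exposure against a pre-run-in baseline, so they cannot attribute a laboratory grade to the SC regimen

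*SAP*

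**What the plan says.** **Baseline.** SAP Section 6 (Definitions) sets one baseline: "For the analysis of all endpoints, baseline will be defined as the value measured on day 1 of the first cycle of blinatumomab". If that value is missing, the latest value before therapy is used. No baseline before SC is defined.

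**Laboratory tables.** SAP 10.5.2.1 will present "The number and percentage of subjects experiencing treatment emergent laboratory toxicities with worst post dose CTCAE grades" at four thresholds. It adds that the "number and percentage of subjects experiencing 1, 2, 3 and 4 worsening CTCAE grade shifts from baseline will be presented". There are also shift tables to the maximum post-dose grade for selected parameters, and optional summaries of change to the post-dose maximum or minimum. None of these states a time window or a route.

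**Treatment-emergent.** SAP Section 6 defines the term for adverse events only, as an event that "starts on or after first dose of blinatumomab through 30 days after the last dose of blinatumomab".

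**Route split elsewhere in the SAP.** For adverse events (10.5.1): "Tables with AEs as above will be produced for period 1 for SC and cIV dosing separately". For exposure (10.5.6): "Descriptive statistics will be produced to describe the exposure to investigational product by dosing schedule for cIV and SC separately". PK and PD summaries (10.7 and 10.8) are also grouped by route.

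**Grouping.** SAP 10.1 says: "Data will be summarized by dose cohort and by time as appropriate". SAP 7.1 instead assigns dose-escalation subjects to the first blinatumomab dose they received. Read literally, that is 9 µg/day cIV for every Period 1 subject.

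**Design.** Protocol 3.1.1 gives every Period 1 cohort the same cIV steps in weeks 1 to 3, SC in week 4, and cIV again in weeks 5 and 6. An optional Cycle 2 after Period 1 is cIV.

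**The concern.** The primary objective is the safety of SC dosing. A Period 1 subject receives SC in one week, between two stretches of cIV that are the same in all cohorts. A table that takes each subject's worst grade over everything after day 1 cannot say on which route that grade arose. A grade reached in the run-in is a floor: an SC-week grade at or below it does not change the table entry. A grade reached on cIV in weeks 5 and 6, or in Cycle 2, counts in the same way.

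The denominators are mixed as well. The safety tables use everyone who received blinatumomab. Protocol 3.3 expects about 20% of subjects to discontinue early, in Period 1 during the cIV run-in. Protocol 6.2.1.4.2 also lets some subjects finish on cIV alone after two or more DLTs in their cohort. Such subjects would count in a cohort's laboratory table without having had SC.

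At stake is the one summary of laboratory toxicity incidence, in a study meant to describe SC safety.

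**Working it through.** The documents state no figure on this point, so there is none to reproduce. The check is a count of draws and days, followed by an illustration of the dilution under assumed rates.

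**1. Scheduled draws.** Protocol Table 3, hematology and chemistry rows, after day 1, for a subject who stops after Cycle 1:

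| Phase | Days | Draws | Share of 12 |
|---|---|---|---|
| cIV run-in | 2, 8, 9, 15, 16 | 5 | 42% |
| SC week | 22, 23 | 2 | 17% |
| Day 29 or later | 29, 30, 37, 43, EOS | 5 | 42% |

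Table 3 does not say whether the day 22 draw precedes the first SC dose, or whether the day 29 draw precedes the cIV restart. Only day 23 is certain to follow an SC dose and precede the restart. Draws that reflect SC before cIV resumes therefore number 1 (day 23 only) to 3 (if day 22 is post-dose and day 29 is pre-restart). No draw is scheduled on days 24 to 28.

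**2. On-drug days, cohorts 1 to 3.** Run-in 21, SC 5, later cIV 14, total 40. SC share: 5/40 = 12.5%. With a 42-day cIV Cycle 2: 5/(40 + 42) = 5/82 = 6%.

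**3. Dilution.** Let q be the chance that a subject reaches grade 3 or higher in the cIV phases, assumed equal in all cohorts, and s the chance of doing so in the SC week. If the two are independent, the whole-course rate is

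1 − (1 − q)(1 − s),

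and the difference between cohorts A and B is (1 − q)(s_B − s_A).

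Take s_A = 10% and s_B = 50%, a true difference of 40 points. These rates and the values of q are assumptions.

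| q | Table rate A | Table rate B | Difference shown |
|---|---|---|---|
| 10% | 19% | 55% | 36 points |
| 50% | 55% | 75% | 20 points |
| 80% | 82% | 90% | 8 points |
| 100% | 100% | 100% | 0 points |

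Under independence the SC difference shrinks by the factor (1 − q) and disappears only as q approaches 100%. Dependence can make this worse. At q = 50%, if every SC-week event fell in a subject who also had one on cIV, both table rates would be 50% and the difference 0.

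**4. Coagulation.** Table 3 schedules it only at screening and at EOS. It has no scheduled run-in or SC-week value, so neither the mixing argument nor an SC table applies to it.

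**The case against.** The strongest reply is that SC laboratory safety is covered elsewhere. Period 1 DLTs are confined to week 4 and are listed and summarized. Laboratory changes that need intervention become adverse events, and those tables are split by route. SAP 10.5.2.1 itself gives full listings, a grade 3 or higher listing with the subject's other values for that parameter, and by-visit summaries for selected parameters. The DLRT receives laboratory listings by cohort and individual line plots. No dosing or MTD decision is tied to the worst-grade tables. The whole-course window is also inferred: 10.5.2.1 gives no end point.

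Much of this stands, and it limits the consequence. It does not supply the missing summary. The DLT definition (Protocol 6.2.1.2.3) excludes grade 3 and 4 lymphopenia, and also laboratory values of grade 3 or higher that respond and resolve to grade 1 or less within 7 days. An asymptomatic grade 3 value that needs no intervention may never become an adverse event. By-visit changes still run from day 1, and a listing is not an incidence. No planned output gives the incidence of laboratory toxicity in the SC week by cohort.

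A reader might go further and infer that the tables describe the run-in and not SC, that the run-in fixes the worst grade, or that cohort differences would be mostly run-in noise. The documents do not support this. Run-in draws are 5 of 12, not a majority. A run-in grade sets a floor that a worse SC value still passes. Nor does the share of draws outside the SC window (9/12 to 11/12, or 75% to 92%) measure the effect: a worst grade is a maximum, unscheduled values also enter, and subjects are inpatients throughout SC dosing, so extra draws are possible.

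**Conclusion.** The point holds in a limited form. The Period 1 hematology and chemistry worst-grade and shift tables combine run-in, SC week, later cIV and, on the natural reading, cIV Cycle 2, all against a baseline taken before the run-in. They cannot attribute a grade to the SC regimen. Differences between SC cohorts are diluted, not erased, unless nearly all subjects reach the grade on cIV or SC events are confined to subjects already affected on cIV.

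The size cannot be stated, because neither document gives laboratory toxicity rates on cIV. The dilution figures rest on assumed rates, independence and an equal cIV rate in all cohorts. The draw counts rest on Table 3 alone and omit unscheduled values.

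This weakens the reporting of SC safety. It does not affect dose decisions, which rest on DLTs and DLRT review. It does not extend to coagulation.

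**What to change.** Add to SAP 10.5.2.1, for Period 1 hematology and chemistry, the split that 10.5.1 already makes for adverse events:

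- **cIV run-in table:** day 1 baseline; values up to the end of the run-in.
- **SC table:** subjects who received SC, grouped by SC dose cohort. Baseline is the last value before the first SC dose. The window runs from after that dose to the last value before cIV restarts, including unscheduled values.
- **Whole-course table:** keep it, labeled as covering both routes.

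Also state how the day 22 and day 29 draws are classified. Protocol 7.3.14 requires collection times in site source documents but does not say that they reach the database. If day 22 proves to be post-dose, the last scheduled value before SC is day 16. Say which window applies to a subject who returns to cIV after an SC-week event and later resumes SC, as Protocol Table 2 allows.

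Reconcile the SAP 7.1 grouping by first dose received with the dose-cohort grouping in 10.1. Leave coagulation out of the split.

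The cost is SAP wording and a few extra tables from data already collected. The downside should be stated with the tables. The SC table rests on 1 to 3 scheduled draws per subject in cohorts of about 6. Its baseline follows three weeks of cIV and a 12-hour break, so cIV effects may carry over. Closing the window at the cIV restart may miss late SC effects.
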